### **5.1.3 Subject Exclusion Criteria**

The subject must be excluded from participating in the trial if the subject:

1. Has progressed to dementia due to AD per investigator diagnosis in the initial 104-week study.
2. Is in imminent risk of self harm, based on clinical interview or on the Columbia Suicidality Severity Rating Scale (C-SSRS), or of harm to others in the opinion of the investigator. Subjects who report suicidal ideation with intent, with or without a plan (e.g., suicidal ideation item 4 or 5 on the C-SSRS) in the past one (1) month or suicidal behavior in the past six (6) months should be excluded. Such subjects will be permitted to rescreen for entry into this study once in the Investigator's opinion, this risk of harm to self or others is no longer present.

3. Has developed a recent or ongoing, uncontrolled, clinically significant medical or psychiatric condition that precludes participation in this protocol in the judgment of the investigator.
4. Based on results from the EOT Visit (Visit 12) in the initial 104-week trial has results of clinical laboratory tests (complete blood count [CBC], blood chemistries, and urinalysis) that are clinically unacceptable to the investigator. However, it is recognized that lab results will not be available at Visit 12/12B if they occur on the same day. Therefore, such subjects may be enrolled prior to receiving these results; upon their receipt of the lab results, if the PI feels they are clinically unacceptable the subject should be discontinued.
5. Based on the results from the EOT Visit (Visit 12) has results of a physical examination, and vital signs that are clinically unacceptable to the investigator.
6. Has developed a form of dementia that is not Alzheimer's Disease, including but not limited to, dementia due to HIV infection, head trauma, vascular disease, Parkinson's disease, frontotemporal dementia, or Huntington's disease, as determined by the investigator.
7. Anticipates receiving any of the treatments listed in [Table 1](#) during the current trial.

Table 1 Prohibited Medications

Prohibited Medications, Supplements, and Other Substances
Anti-amyloid agents (e.g., tarenflurbil, tramiprosate)
Anti-amyloid antibodies (e.g., solanezumab)
Anti-amyloid vaccine (Subjects who received placebo only in a vaccine trial may participate in this trial.)
CYP3A4 inducers (strong) including: Rifampicin and St. John's Wort, phenytoin, carbamazepine Exceptions: Use of the following is acceptable: topical use; short-term (<2 weeks) oral treatment during the trial; use of oral St. John's Wort <300 mg three times a day during the trial, regardless of duration.

NOTE: This is not a complete list of excluded medications. Contact the Sponsor if there is a question about a specific medication.

7. Has progressed to dementia due to AD per investigator diagnosis in the initial 104-week study.

## 5.2 Trial Treatments

The treatments to be used in this trial are outlined below in [Table 2](#).

Table 2 Trial Treatments

Drug	Dose/Potency	Dose Frequency	Route of Administration	Regimen/Treatment Period	Use
MK-8931	12 mg tablet	Once daily	Oral	Up to 260 weeks	Investigational
MK-8931	40 mg tablet	Once daily	Oral	Up to 260 weeks	Investigational

Subjects who received the 12 mg or 40 mg dose in the initial 104-week trial will continue to receive the same dose in this long term trial. Subjects who received placebo during the initial 104-week trial will receive the 40 mg dose during this long term trial.

### **5.2.1 Dose Selection/Modification**

#### **5.2.1.1 Dose Selection**

The rationale for selection of doses to be used in this trial is provided in Section 4.0 – Background & Rationale. There are no specific calculations or evaluations required to be performed in order to administer the proper dose to each subject.

#### **5.2.2 Timing of Dose Administration**

The trial medication should be administered by the subject, by the subject’s trial partner, or by a caregiver. Each subject should take one tablet at approximately the same time each day without regard to food. For each treatment group, one tablet equals one dose of trial medication as summarized below:

- 12/12 group: MK-8931 12 mg (one tablet)
- 40/40 and placebo/40 groups: MK-8931 40 mg (one tablet)

If a subject misses a dose, the subject may take the dose later in the day and should continue with the regular dosing schedule by taking the next dose at the usual time the next day. Any changes in dosing schedule should be noted by the subject or subject’s trial partner and recorded by the site at the next visit. Subjects should not take more than one dose on the same calendar day.

With the exceptions of any subjects enrolled to a dose that is dropped for reasons of safety or tolerability, there will be no adjustments to the dose of any subject in the trial.

#### **5.2.3 Trial Blinding/Masking**

A double-blind/masking technique will be used. MK-8931 12 and 40 mg tablets will be packaged identically so that treatment blind/masking is maintained for the subject and the investigator. The Sponsor will be unblinded at the completion of the initial 104-week trial.

See Section 7.1.4.2, Blinding/Unblinding, for a description of the method of unblinding a subject during the trial, should such action be warranted.

### **5.3 Concomitant Medications/Vaccinations (allowed & prohibited)**

Medications or vaccinations specifically prohibited in the exclusion criteria are not allowed during the ongoing trial. Listed below are some specific restrictions for concomitant therapy or vaccination during the course of the trial. If there is a clinical indication for one of these or other medications or vaccinations specifically prohibited during the trial, discontinuation from trial therapy or vaccination may be required. The investigator should discuss any questions regarding this with the local Clinical Monitor. The final decision on any supportive therapy or vaccination rests with the investigator and/or the subject's primary physician. However, the decision to continue the subject on trial therapy or vaccination schedule requires the mutual agreement of the investigator, the Sponsor and the subject.

#### **5.3.1 Prohibited Medications**

The subject must not take the treatments listed in [Table 1](#) during this trial.

During the trial, initiation of treatment with medications known to be associated with substantial increased risk of Stevens-Johnson Syndrome or toxic epidermal necrolysis should be avoided when possible. Subjects who have been safely treated with at least one routine course of treatment with these medications in the past are exempted from this requirement. Examples of such medications are included below. The Sponsor should be consulted for questions about specific medications.

- trimethoprim-sulfamethoxazole, azithromycin, allopurinol, phenobarbital, oxicam NSAIDS (e.g., celecoxib, valdecoxib, meloxicam), carbamazepine, phenytoin, valproic acid, nevirapine, lamotrigine, and chlormezanone

#### **5.3.2 Allowed Medications**

Medications, supplements, and other substances allowed during the trial include, but are not limited to, those listed in [Table 3](#). Note that the use of any concomitant medication must relate to the documented medical history, prophylaxis, or an adverse event of the subject. **Initiation and change of dose of cholinesterase inhibitors and memantine are allowed in this trial.**

Table 3 Medications, Supplements, and Other Substances Allowed During the Trial

Allowed Medications, Supplements, and Other Substances
Acetylcholinesterase inhibitors (e.g., donepezil, tacrine, rivastigmine, galantamine)
Memantine
Huperzine A
Vitamin E
Herbal supplements from Ginkgo biloba , ginseng, Huperzia serrata (Qian Ceng Ta)
Medical foods/supplements (e.g., Axona ® , Souvenaid ® )
Estrogens and estrogen-like compounds
Antihypertensives
Nonsteroidal anti-inflammatory drugs (NSAIDs)
Cyclooxygenase 2 inhibitors
Neuroleptics
Antidepressants
Carbidopa/levodopa and dopamine agonists
Pregabalin and gabapentin
Rifampicin and St. John's Wort: Topical use, short-term (<2 weeks) oral treatment during the trial, use of oral St. John's Wort <300 mg three times a day during the trial, regardless of duration.
Selective H1 blockers, selective H2 blockers, and topical anti-pruritic treatments for treatment of rash during the trial, as specified in the Rash Guidance Document.

#### 5.4 Rescue Medications & Supportive Care

No rescue or supportive medications are specified to be used in this trial.

#### 5.5 Diet/Activity/Other Considerations

Subjects who are provided non-pharmacological treatments, such as day care, may continue these through the trial. The frequency should not change unless medically indicated. Day care attendance on the day before clinic visits and cognitive testing should remain stable through the protocol.

#### 5.6 Subject Withdrawal/Discontinuation Criteria

Subjects may withdraw consent at any time for any reason or be dropped from the trial at the discretion of the investigator should any untoward effect occur. In addition, a subject may be withdrawn by the investigator or the Sponsor if enrollment into the trial is inappropriate, the trial plan is violated, or for administrative and/or other safety reasons. Specific details

regarding discontinuation or withdrawal procedures are provided in Section 7.1.4 – Other Procedures.

In this trial, a subject may temporarily discontinue from treatment under certain conditions specified in the protocol (e.g. in follow-up to imaging abnormalities or rash; refer to Sections 7.1.2.2.6 and Rash Guidance Document for details) but continue to participate in the regularly scheduled activities, as long as the subject does not withdraw consent. Given the exploratory nature of this long term trial's endpoints, subjects who permanently discontinue from treatment will be discontinued from the trial.

A subject must be discontinued from the trial for any of the following reasons:

- The subject or legal representative (such as a parent or legal guardian) withdraws consent.
- The subject has a medical condition or personal circumstance which, in the opinion of the investigator and/or Sponsor, places the subject at unnecessary risk through continued participation in the trial or does not allow the subject to adhere to the requirements of the protocol.

A subject must be discontinued from treatment (but may continue to be monitored in the trial) for any of the following reasons:

- Elevated ALT, AST, or T-BIL meeting any one of the following criteria:
  - ALT or AST  $\geq 8$  x ULN;
  - ALT or AST  $\geq 5$  and  $< 8$  x ULN for more than 2 weeks;
  - ALT or AST  $\geq 3$  x ULN and T BIL  $\geq 2$  x ULN at the same visit;
  - ALT or AST  $\geq 3$  x ULN with the appearance of symptoms indicating hepatitis (e.g., worsening fatigue, nausea, vomiting, right upper quadrant pain or tenderness, fever, rash, or eosinophilia).

Exception: If elevations are determined to be due to some other medical condition, subject may resume trial medication with Sponsor approval.

- An imaging abnormality consistent with intraparenchymal macrohemorrhage appears (see details in Section 7.1.2.2.6);
- QTc prolongation (defined as QTc interval  $> 500$  ms or QTc change from baseline  $> 60$  ms, based on the average of three measurements using the Fridericia formula for correction).
- Exception: If QTc change from baseline (from Visit 1 of the initial 104-week trial)  $> 60$  ms is determined to be due to some other medical condition, or if subject has a new onset of bundle branch block, subject may continue treatment with Sponsor approval.

- The subject develops a form of dementia that is not Alzheimer's Disease, including but not limited to dementia due to HIV infection, head trauma, vascular disease, Parkinson's disease, frontotemporal dementia, or Huntington's disease, as determined by the investigator.
- The subject develops a severe rash confirmed by a dermatologist. For the purpose of this program, a “**severe rash**” is defined as one of the following:
  - A vesicular rash (i.e., one with blistering lesions) that is not clearly caused by herpes simplex virus or contact allergy such as poison ivy AND has EITHER a) extensive body surface area (BSA) involvement OR b) involves oral/mucosal surfaces.
  - Stevens Johnson Syndrome, erythroderma, or toxic epidermal necrolysis
  - DRESS Syndrome.
- The subject develops an uncontrolled AND clinically significant rash defined as follows:
  - A clinically significant rash (see Section 7.2.3.2) that is not controlled by topical medications or oral medications such as antihistamines (detailed in the Rash Guidance Document) AND causes intolerable symptoms attributed to study drug.
- The subject’s trial partner is no longer willing or able to participate in the study and a suitable replacement trial partner cannot be found in a reasonable period of time.

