## **5.8 Beginning and End of the Trial**

Each subject is considered to be enrolled when the subject (or the subject’s legal representative) has provided written informed consent in accordance with local requirements.

This long-term trial will start with enrollment of the first subject who completes the initial 104-week trial and chooses to participate in the long term trial. This trial will end after 5 years after the first subject enrolls (260 weeks), or a) when the drug either becomes commercially available (locally), or b) when the MK-8931 program is terminated (whichever comes first). Duration of participation may also be limited based on local regulations. Each subject is considered to have ended participation in the trial when he/she has completed the last protocol-specified contact (e.g., visits or telephone contacts) or has prematurely discontinued from the trial. A subject will be considered a completer of this long-term trial if he/she is still continuing in the trial when the trial is stopped.

A subject is considered to have discontinued after he/she has withdrawn consent or has been discontinued under the conditions specified in Section 7.1.4.1. Given the exploratory nature of the long-term trial, the retrieved dropout approach employed in the initial 104-week trial will be discontinued from this trial. All applicable activities scheduled for the final trial visit should be performed at the time of treatment discontinuation as defined in the long-term trial Flow Chart in Section 6.0.

A subject is considered to have been lost to follow-up if he/she is unable to be contacted by the investigator. The end of participation for a subject lost to follow-up is the last known contact (e.g., visit or telephone contact).

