#### 7.1.4 Other Procedures

##### 7.1.4.1 Withdrawal/Discontinuation

When a subject discontinues/withdraws prior to trial completion, all applicable activities scheduled for the final trial visit should be performed at the time of discontinuation. Any adverse events which are present at the time of discontinuation/withdrawal should be followed in accordance with the safety requirements outlined in Section 7.2 - Assessing and Recording Adverse Events. Subjects who permanently discontinue from treatment will be discontinued from the trial.

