Three supportive analyses will be conducted on the primary efficacy endpoint. These analyses will be conducted to assess the effect of 1) missing data using a pattern-mixture model “tipping-point” approach, which is intended to provide a measure of robustness in the (unobservable) event that a larger-than-expected proportion of the missing data be missing-not-at-random (MNAR) 2) the use of off-regimen data after the subject has permanently discontinued trial medication or after the subject has initiated AChEIs and 3) analysis using the cLDA model on the MFAS population.

For the first sensitivity analyses (tipping-point), the model-based estimates of the mean treatment difference on the change scores, along with the corresponding confidence intervals and p-values will be provided for a range of  $c$  values which have been subtracted from the values imputed for the active arms (see Section 8.2.7.5 for more details). Of specific interest is the smallest  $c$  value that, for a given endpoint, transforms a “statistically significant” result to a “non-statistically significant” result (per the pre-defined  $\alpha$ -level used in the initial 104-week trial).

For the second sensitivity analysis (excluding observations obtained after study medication discontinuation or after the initiation of AChEIs), the model-based estimates of the mean treatment difference on the change scores, along with the corresponding confidence intervals and p-values will be provided.

For the third sensitivity analysis (cLDA model on the MFAS population), the analysis of the primary efficacy endpoint will be conducted using a constrained longitudinal data analysis (cLDA) method proposed by Liang and Zeger [28]. This model assumes a common mean across treatment groups at baseline and a different mean for each treatment at each of the post-baseline time points. The response vector consists of baseline and the values observed at each post-baseline time point. The model-based estimates of the mean treatment difference on the change scores, along with the corresponding confidence intervals and p-values will be provided as obtained using the cLDA model, with all of the same covariates that were included in the primary model (now excluding the terms for baseline and baseline-by-time interaction). An unstructured covariance model will be used.

Table 6 Analysis Strategy for Primary Endpoints

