### **8.2.8 Statistical Methods for Safety Analyses**

Subjects from all three arms (40 mg / 40 mg, 12 mg / 12 mg, Pbo / 40 mg) will be included in the safety analyses. Where applicable, treatment comparisons will be conducted between the 40 mg / 40 mg and Pbo / 40 mg arms, as well as between the 12 mg / 12 mg and Pbo / 40 mg arms.

Safety and tolerability will be assessed by clinical review of all relevant parameters including AEs, laboratory tests, vital signs, and ECG measurements. The primary approach for all safety analyses will be an On Drug approach, i.e., one that includes only those observations obtained from the first dose through 14 days after the last dose of study medication. A supportive approach will include all post-treatment observations, including those observations obtained more than 14 days after the last dose of study medication.

The analysis of safety results will follow a tiered approach (Table 7). The tiers differ with respect to the analyses that will be performed. Safety parameters or adverse experiences of special interest that are identified a priori constitute “Tier 1” safety endpoints that will be subject to inferential testing for statistical significance with p-values and 95% confidence intervals provided for between-group comparisons. Other safety parameters will be

considered Tier 2 or Tier 3. Tier 2 parameters will be assessed via point estimates with 95% confidence intervals provided for between-group comparisons; only point estimates by treatment group are provided for Tier 3 safety parameters.

Adverse experiences (specific terms as well as system organ class terms) and predefined limits of change in laboratory, vital signs, and ECG parameters (see Section 12.3) that are not pre-specified as Tier-1 endpoints will be classified as belonging to "Tier 2" or "Tier 3", based on the number of events observed. Membership in Tier 2 requires that at least 1% of the subjects in any treatment group exhibit the event; all other adverse experiences and predefined limits of change will belong to Tier 3.

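### The protocol gives conflicting rules on following subjects who stop treatment for good, and ends their follow-up as exploratory although Week 130 CDR-SB is the primary efficacy endpoint

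*Combined protocol and SAP*

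**What the plan says.** Section 5.6 states the exit rule with its reason: "Given the exploratory nature of this long term trial's endpoints, subjects who permanently discontinue from treatment will be discontinued from the trial". Section 7.1.4.1 repeats it: "Subjects who permanently discontinue from treatment will be discontinued from the trial". Section 5.8 adds that "the retrieved dropout approach employed in the initial 104-week trial will be discontinued from this trial".

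Section 5.6 then introduces a list of liver, imaging, QTc, dementia, rash and trial-partner reasons with the words "A subject must be discontinued from treatment (but may continue to be monitored in the trial".

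The analysis plan in Section 8 refers in two places to data after treatment has stopped. One of the three supportive efficacy analyses in Section 8.2.7.1 concerns "the use of off-regimen data after the subject has permanently discontinued trial medication", or data after an acetylcholinesterase inhibitor (AChEI) was started. Section 8.2.8 says of safety: "A supportive approach will include all post-treatment observations, including those observations obtained more than 14 days after the last dose of study medication".

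Sections 3.1 and 8.2.3.1.1 make the Week 130 change in CDR-SB a primary objective and the primary efficacy endpoint.

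**The concern.** A site with a subject who has stopped drug for good can find support in Section 5.6 both for ending participation and for continuing it. The reason offered for ending it does not fit the endpoint most affected. The plan protects Week 130 elsewhere: Section 4.2.1.1 keeps a sponsor group blinded with that time point in mind, and Section 7.1.2.3 has ratings recorded for review through Week 130.

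Two things are at stake.

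- **Bias.** Placebo/40 subjects meet the drug for the first time in the extension, while continuers on active drug have normally tolerated it for two years (Section 5.1.2). Loss could therefore differ between arms. If placebo/40 loses subjects who are doing worse than predicted, that arm looks better than it is and the difference is understated. Loss of such subjects from 40/40 does the opposite.
- **Estimand.** The initial 104-week trial (Part I) used retrieved-dropout follow-up, and all its observations enter the Week 130 model. Extension data end at treatment stop. One model thus mixes two policies, one before Week 104 and one after.

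**Working it through.** **1. Is the contradiction real?** Some reasons on the must-stop list allow dosing to resume, and Section 5.6 lets subjects on a temporary stop attend scheduled visits. Those cases can be reconciled. Macrohemorrhage cannot: it is on the list, and Section 7.1.2.2.6 bars any further dosing. The same subject is required to leave and permitted to stay.

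**2. What CDR data remain?** In the flow chart (Section 6.0) the first scheduled extension CDR is at Week 130. A subject who stops earlier has only the early-termination CDR. That counts at Week 130 only within the ±6-week analysis window of Section 8.2.4.1, so from about Week 124. If stops were spread evenly over the 26 weeks (assumption), 6/26 = 23% would fall in the window before Week 130.

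**3. How many subjects?** Inputs from Section 8.2.11.1.2: 450 per arm, dropout 25% at Week 104 and 37% at Week 130, and 90% of completers continuing.

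- Check on the plan's projection: 1350 × 0.75 × 0.90 = 911.25, against about 912 in Section 1.0.
- Entering, per arm: 450 × 0.75 × 0.90 = 303.75.
- With Week 130 data, per arm: 450 × 0.63 = 283.5.
- Lost inside the extension: 20.25 per arm, 60.75 (about 61) over three arms. As a share of entrants, 20.25/303.75 = 6.7%.
- Missing at Week 130 for any reason: 450 × 0.37 = 166.5 per arm. The extension share is 20.25/166.5 = 12%.

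**4. Power.** The stated 73.9% came from simulation with an effect that is not given, so it cannot be reproduced independently. I back-solved the effect, using Table 8 and assuming a two-sided test at 0.02495.

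- ANCOVA SD: 3.05 × √(1 − 0.359²) = 2.847.
- Effect: (2.242 + 0.640) × 2.847 × √(2/283.5) = 0.689, which is 32% of the 2.13 progression. Across SD choices and one- or two-sided tests it runs from 0.622 to 0.738.

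Following all 20.25 per arm gives n = 303.75. The average effect becomes 0.689 × (283.5 + k × 20.25)/303.75, where k is the share of the effect kept off drug:

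| k | Power |
|---|---|
| 1 | 77.1% |
| 0.5 | 74.0% |
| 0 | 70.6% |

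**5. Bias.** Assume that all 20.25 lost subjects in one arm are 1 point worse than the model predicts.

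- Averaged over all randomised subjects in the arm: 20.25/450 = 0.045, or 0.045/0.689 = 6.5% of the implied effect.
- Averaged over entrants: 20.25/303.75 = 0.067, or about 10%. For this figure to apply to the primary model, which also covers subjects who never enter the extension, the shift must carry over to them.

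**6. The supportive analyses.**

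- *Safety after 14 days.* Adverse events are generally collected for 14 days after the last dose (Section 7.2). One telephone call follows at 14 days plus up to a week (Section 6.0, footnote f). Section 8.2.8 leaves Part I post-dose data out unless otherwise noted. What remains is that call, related serious events reported late (Section 7.2.3.1) and any interruptions on trial. The approach has little to use.
- *Off-regimen efficacy.* Only the extension part of the discontinuation trigger is thin. AChEIs may be started during the extension (Section 5.3.2), and Part I off-treatment observations are in the model.

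**The case against.** Ending retrieved-dropout follow-up is a disclosed decision. The plan has no formal hypotheses and says openly that Week 130 is underpowered. Exit is stated in Sections 5.6 and 7.1.4.1 and fits Section 5.8, against one permissive parenthesis. Most missing Week 130 data (88%) arise in Part I or from not entering, which this rule does not touch. A tipping-point analysis already probes data missing not at random.

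Much of this stands, and it limits the weight of the point. It does not remove the contradiction, and having no formal hypotheses does not turn a primary endpoint into an exploratory one. The tipping-point analysis (Section 8.2.7.5) shifts only the active arms and leaves the control group missing at random, so it does not examine worse-than-predicted losses in placebo/40.

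A reader might go further in four ways that the documents do not support:

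- That the off-regimen efficacy analysis would nearly duplicate the primary one. Its AChEI trigger and its Part I data remain.
- That follow-up would lift power to 77%. That is the best case, with everyone retrieved and the full effect kept off drug. Power could also fall below 73.9%.
- That this rule loses 61 subjects. That figure is a ceiling covering all dropout after entry, including withdrawn consent and loss to follow-up.
- That sites will in fact diverge. The text permits it, but nothing in the documents shows it.

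**Conclusion.** The point holds as a contradiction in the follow-up rules, with a justification that does not fit the primary endpoint. Its numerical reach is modest: at most about 20 subjects per arm, some of them unrecoverable or already covered by an in-window termination visit. The possible bias of 0.045 to 0.07 rests on two assumptions: a 1-point departure confined to one arm, and an effect back-solved from the stated power. No difference in dropout between arms is documented. Full follow-up would leave power between about 70.6% and 77.1%, so power is not a reason for the change. Consistency of the estimand and protection against bias are. The correction is worth making because it is cheap.

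**What to change.** 1. Reconcile Sections 5.6, 5.8, 7.1.2.2.6 and 7.1.4.1 so that they state one follow-up rule for subjects who permanently stop treatment. Which events stop treatment is not at issue here.
2. Remove the exploratory justification as far as it concerns the primary endpoint.
3. As a data-collection change only, keep the scheduled Week 130 CDR for subjects off drug who have not withdrawn consent. Follow-up after Week 130 can stay as planned. Section 8.2.4.1 does not exclude such observations if its dosing requirement around Week 104 is met, so the primary model would take them without redefinition.
4. Align the supportive safety approach in Section 8.2.8 with the data actually collected more than 14 days after the last dose.

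The cost is protocol wording and at most about 61 visits that are already on the schedule. The downside is the burden of those visits for subjects no longer on drug.
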